9.1 STATISTICAL HYPOTHESES AND PROPOSED ANALYSES

Specific Aim 1. Descriptive statistics (frequencies, min, max, mean, standard deviation) and contingency table analysis will be performed to identify any possible coding errors. Data inconsistencies identified will be sent back to sites for correction. We will calculate the proportion and exact 95% confidence interval (CI) of CASH cases among all CA cases at each SCA site and overall. Baseline characteristics will be summarized using chi-square tests for categorical variables and t-tests for continuous variables. EQ-5D measures are scored on the T-score metric, with a mean of 50 and standard deviation (SD) of 10 in a referent population (mild, moderate, and severe impairment is defined as 0.5-1.0 SD, 1.0-2.0 SD, or 2.0+ worse than the mean, respectively). Spearman correlation coefficients will be calculated between mRS and Euro-QoL and PROMIS29 scales, and mean scores of Euro-QoL and PROMIS29 will be stratified by mRS levels. This analysis will allow us to determine ceiling effects of scores and how well the Euro-QoL and PROMIS29 data are distributed in CASH cases. Functional and QOL scores shall also be analyzed by pre-defined subgroups (sex, genotype and lesion location), to inform stratification or the need for adaptive randomization in clinical trials.

Specific Aim 2. This will follow the same design for QSM and DCEQP data acquired using these phantoms. A $p<0.05$ will be considered a failure, or significant non-zero difference. The accuracy of QSM and DCEQP values will be assessed at each of the sites participating in the FUBV arm by estimating the coefficient of determination r^2 between the observed and known phantom values, with $r^2 \geq 0.95$ needed to validate accuracy of each technique³⁵. The Pearson's correlation coefficients r of the FUBV subjects will also be compared using Fisher transformation. The precision of QSM and DCEQP measurements will be tested by comparing two separate measurements acquired at each site, using a paired t-test (7 ferumoxytol concentrations acquired twice by QSM, and 7 permeability values simulated with the phantom twice by DCEQP). The reproducibility of phantom measurements will be evaluated by comparing the QSM and DCEQP simulation values acquired at New Mexico and Mayo Rochester against the values obtained at Chicago, and one another, using a two-sample t-test.

Specific Aim 3. Time to recurrent SH will be analyzed using Kaplan Meier method and Cox proportional hazards regression approach. Rates of recurrent SH/patient/year from initial SH qualifying event, and SH/patient/year from enrollment (potentially more relevant for trial modeling) will be estimated along with 95% CIs. Changes in mean lesional QSM and K_i during 1 and 2-year epochs will be compared using paired t-test or Wilcoxon signed rank test to assess changes within patients over time, including 95% CIs. To test predictive, monitoring or surrogate outcome hypotheses, two sample t-test or Wilcoxon rank sum test will be used to compare such changes between patients with and without recurrent SH. Categorical variables such as proportions of patients with a drop in mRS score ≥ 1 point, difference in EQ-5D and PROMIS 29 scores, NIHSS scores, between patients with and without recurrent SH will be compared using Chi-square or Fisher's exact test. Associations of baseline characteristics (sex, lesion locations, familial/sporadic) and recurrent SH as a binary outcome (yes/no) will be assessed using

univariable and multivariable logistic regression and reported as odds ratios and 95% CIs. Depending on the number of recurrent SH over the 2-year period, we may analyze re-bleeds as a continuous outcome and the associations of baseline features or biomarkers assessed using linear regression. Performance of final model(s) will be assessed using r^2 in the case of linear regression, area under the curve (AUC) and Hosmer Lemeshow goodness of-fit test⁵⁵ in the case of logistic regression, or concordance index in the case of Cox proportional hazards regression. AUCs between various models (univariable) will be compared using the method proposed by DeLong et al⁵⁶. For biomarkers, we will create a binary variable (yes/no) depending on whether the % change in mean lesional QSM or K_i during 1-year epochs exceed previously defined respective thresholds (+ 5.8% QSM and +39.6% for K_i)³³ that were significantly associated with new clinical events at high sensitivity and specificity in previously stable lesions. We will then assess the association of this newly created variable (“biomarker event”) with SH rate treated as continuous (using two sample t-test or Wilcoxon rank sum test) and binary (using Chi-square or Fisher’s exact test) outcomes of interest. Finally, we shall compare the sensitivity/specificity of changes in mRS, QOL, and NIHSS scores, and lesional QSM and K_i in relation to SH during the same epochs, using McNemar’s test with SH (yes/no binary) as the reference standard. All tests will be 2-sided and p-values <0.05 considered statistically significant.

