Knowledge Gaps Regarding the Prevalence of CASH and Baseline Characteristics. For planning and executing multi-site clinical trials, it is unclear what fraction of CA patients would meet the likely trial eligibility criteria of SH within the prior year with an unresected lesion. That prevalence varied between 10-25% in the three largest ongoing CA research databases at U.S. institutions, with different referral patterns and enrollment criteria. This might vary further at other institutions, and with systematic screening. **Prospective prevalence of CASH in systematic screening of CAs, and enrollment rates at multiple sites are not known.** These data are essential for the proper design of clinical trials, including the number of prospective sites needed. It is further unclear how CASH cases might vary by age, sex, familial versus sporadic, lesion size and location, associated venous anomaly, past bleeds, and baseline disability. These features varied or were not assessed consistently in the 3 active prospective CA research databases in the U.S. More importantly, the **assessment of these features at multiple sites has never been harmonized or adjudicated. Further, it is unclear what functional status and Quality of Life (QoL) instruments best capture the clinical impact of CASH.** Inclusion/exclusion criteria and stratification for these characteristics will be important in clinical trials, as they will impact natural risk, and potentially the effect of putative therapies. These critical knowledge gaps will be addressed in Specific Aim 1 of this proposal.

Opportunities and Challenges with Novel Biomarkers Linked to Clinical Bleeding in CAs.

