9.2 SAMPLE SIZE DETERMINATION

Screening and Clinical Assessment (SCA) Arm: We calculated the width of the exact 95% CI for detecting CASH cases, varying the prevalence from 10% to 25% based on the range in preliminary data, and total sample sizes screened from 500 to 1,500. Based on these sample size models, we propose recruiting 200 CASH cases for the SCA arm of this project, to be enrolled during years 2-5, an average of 50 cases/year at all sites, and less than one case/site/month. Assuming a 15% prevalence of CASH cases (the average in three ongoing registries), a screening sample size of 1,333 would be required over a 4-year period (333 cases to be screened/year) to detect 200 CASH cases \pm 2% (i.e., 13% to 17%). Even if the true prevalence is lower (e.g. 10%) or higher (25%), we will have excellent precision to within \pm 1.5% to 2.5%, respectively, corresponding to 134 - 334 CASH cases for the same screening sample size. These CASH sample sizes will also allow flexibility in describing the proportion of important subgroups (i.e. sex, lesion location, genotype), and provide realistic estimates of recruitment at SCA sites (screened/enrolled ratio).

The 7 main sites are all high-volume CA clinical centers, with demonstrated ability to screen the requisite number of cases. Their recent clinical activity is demonstrated by the number of CA cases (n) seen over a 12-month period with diagnosis ICD9 228.02 on initial or follow-up visits at each of the institutions: 1) University of Chicago (n=106), 2) Mayo Clinic-Rochester (n=70), 3) University of New Mexico (n=80), 4) University of Utah (n=40), and 5) Barrow Neurological Institute, Phoenix (n=200); TOTAL (n=496). We would need to screen 1,333 CA cases over a 4-year period at the 5 sites (333 CAs screened each year), in order to identify and enroll 200 CASH cases, based on the estimated prevalence of 15% CASH cases among overall CA cases. This is a very realistic target, with 496 CAs actually evaluated per year at the 5 sites for the SCA arm. To help meet the target enrollment, The University of California- San

Francisco (n=70) was added as a recruitment site in February 2019 and Johns Hopkins University (n=150) will be added in 2020. If we do not meet our target enrollment of CASH cases, we may add additional, yet to be decided on, sites.

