9.3 POPULATIONS FOR ANALYSES

Cavernous angiomas with symptomatic hemorrhage (CASH) are most likely to re-bleed and cause further neurologic sequelae. It would be desirable to develop a drug that stabilizes CASH, and prevent recurrent bleeding. CASH with recent bleed, where surgical resection is not undertaken, are the most likely cases to be followed expectantly per current evidence based guidelines, with clinical equipoise for testing novel therapies to prevent re-bleeding. They are the most likely cases to be targeted for clinical trials.

Appropriate and complete statistical modeling of data collected by the sites for both SCA/FUBV arms are imperative to the planning, development, and completion of a successful Phase III interventional trial. The most critical component is the accurate assessment of the enrollment rates of CASH across several sites, as well as the between-site variability in these estimates. Both within and between sites variability will be used to adequately power a Phase III trial, will be calculated by developing random-effect models along with using appropriate link functions quantifying the rates of CASH in these models.

As a follow-up step, in-depth data analyses will be performed using the demographic, imaging, clinical and biomarker data collected. These are applied to develop models assessing how predictive each of these factors is to the development of recurrent SH. Understanding which factors are most predictive of SH will be crucial in developing a covariate adaptive randomization scheme for the Phase III trial that insures proper balance in these prognostic factors between treatment arms. Finally, statistical assessments of changes in lesional iron content and permeability biomarkers, QOL, mRS, and NIHSS during follow-up of CASH patients will be performed. Understanding how these measures change over time will be an important step in the process of developing hypotheses on the effect of treatment on these as putative secondary or surrogate outcomes, or as potential composite outcomes.

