We will calculate the proportion and exact 95% confidence interval (CI) of CASH cases among all CA cases at each SCA site and overall. Baseline characteristics will be summarized using chi-square tests for categorical variables and t-tests for continuous variables. Baseline Euro-QoL and PROMIS29 measures will be validated for use in CAs. Euro-QoL and PROMIS29 measures are scored on the T-score metric, with a mean of 50 and standard deviation (SD) of 10 in a referent population (mild, moderate, and severe impairment is defined as 0.5-1.0 SD, 1.0-2.0 SD, or 2.0+ worse than the mean, respectively). Spearman correlation coefficients will be calculated between mRS and Euro-QoL and PROMIS29 scales, and mean scores of Euro-QoL and PROMIS29 will be stratified by mRS levels. This analysis will allow us to determine ceiling effects of scores and how well the Euro-QoL and PROMIS29 data are distributed in CASH cases.

Homogeneity of event rates, biomarker changes, and other endpoints in years 1 and 2. This will be assessed, as it impacts (1) sample size calculations for time averaged assessments of the impact therapies, and (2) whether future trials should be conducted for 1 or 2 years.

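### Section 9.2's ±2-point precision for the overall CASH yield leaves out between-site variation, and the random-effects models of 9.3 are not named as the source of the overall interval

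*Combined protocol and SAP*

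**What the plan says.** Sections 9.1 (Specific Aim 1) and 9.4.1 name one kind of interval for the CASH yield. Section 9.1 says: "We will calculate the proportion and exact 95% confidence interval (CI) of CASH cases among all CA cases at each SCA site and overall". Section 9.4.1 repeats the plan for an "exact 95% confidence interval (CI) of CASH cases among all CA cases at each SCA site and overall".

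Section 9.2 derives its precision from the width of that interval. It varies a single common prevalence and the total number screened. With 1,333 screened and 15% prevalence it expects 200 CASH cases and ±2 points (13% to 17%). It adds: "Even if the true prevalence is lower (e.g. 10%) or higher (25%), we will have excellent precision to within" ±1.5 and ±2.5 points respectively. The calculation contains no term for site.

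Section 4.2 describes the existing evidence: "That prevalence varied between 10-25% in the three largest ongoing CA research databases at U.S. institutions", "with different referral patterns and enrollment criteria". It expects further variation at other institutions and with systematic screening. On the use of the estimate it says: "These data are essential for the proper design of clinical trials, including the number of prospective sites needed".

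Section 9.3 treats enrollment rates and their between-site variability as the most critical component. It says that "Both within and between sites variability will be used to adequately power a Phase III trial" and that these "will be calculated by developing random-effect models along with using appropriate link functions quantifying the rates of CASH in these models". It does not say which estimate or interval the models will report. Sections 9.1, 9.2 and 9.4.1 do not mention them.

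Section 10.1.4 expects confidence intervals for detection rates to feed the assumptions of later trials, without saying which method supplies them.

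**The concern.** A pooled exact binomial interval treats all screened patients as one sample with one underlying probability. If yield differs between sites, the interval still describes the patients screened at these sites. It is too narrow as a statement about average yield across sites of this kind.

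The plan gives reason to expect differences between sites and wants the results for planning other sites. A planner could therefore take 13% to 17% as the uncertainty to carry into a later trial. Section 9.3 has the right kind of model. However, the plan names two methods for one quantity and does not say which is inferential, so the choice could be made after the results are known.

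**Working it through.** **Inputs.** From 9.2: 1,333 screened; prevalence 15% (range 10-25%); listed yearly CA volumes 106, 70, 80, 40, 200, 70 and 150, total 716. The between-site SD is **not in the documents**. Three values are assumed: 2 points (harmonised screening removes most of the spread), 3.75 points (the 15-point database range / 4) and 5 points (range / 3). That range also contains sampling error and differing enrollment criteria, so it is only a guide.

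**1. The plan's own figures (exact Clopper-Pearson).** 200/0.15 = 1,333.

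| Cases/screened | Exact 95% CI | Half-width (points) | Plan states |
|---|---|---|---|
| 133/1,333 | 8.4-11.7% | 1.65 | 1.5 |
| 200/1,333 | 13.1-17.0% | 1.95 | 2 |
| 333/1,333 | 22.7-27.4% | 2.36 | 2.5 |

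The ±2 reproduces as one binomial sample. The ±1.5 at 10% is slightly optimistic, and the ±2.5 at 25% is slightly cautious.

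**2. Half-width for the mean site yield.** Splitting 1,333 by listed volume gives site sizes 197, 130, 149, 74, 372, 130 and 279 (1,331 after rounding). With equal site weights:

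Var = SD²/7 + (1/49) × Σ p(1−p)/nᵢ

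Σ 1/nᵢ = 0.04696, so the second term is 0.1275 × 0.04696/49 = 0.000122. The half-width is t(0.975, 6 df) × √Var, with t = 2.447.

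| Assumed SD (points) | SD²/7 | Var | Half-width (points) |
|---|---|---|---|
| 0 | 0 | 0.000122 | 2.7 |
| 2 | 0.000057 | 0.000179 | 3.3 |
| 3.75 | 0.000201 | 0.000323 | 4.4 |
| 5 | 0.000357 | 0.000479 | 5.4 |

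The SD 0 row shows that part of the widening comes from the t multiplier and equal weighting. To separate this, keep the volume-weighted pooled estimate and z = 1.96: Var = p(1−p)/N + SD²(Σw² − 1/N), with Σw² = 0.179. The half-widths are then 1.9 at SD 0, 2.5 at SD 2, 3.6 at SD 3.75 and 4.6 at SD 5. The between-site term matters under either method.

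**3. Coverage of the pooled exact interval.** Simulation of 40,000 runs, site yields beta-distributed with mean 15%, same site sizes:

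| Assumed SD (points) | Covers mean site yield | Covers the screened cohort's own yield |
|---|---|---|
| 2 | 88% | about 95% |
| 3.75 | 72% | about 95% |
| 5 | 61% | about 95% |

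Logit-normal site yields change the first column by less than 1 point. With only the five sites listed first in 9.2, coverage of the mean is 83% at SD 2 and 52% at SD 5.

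**4. The model already planned.** A logit random-effects model (DerSimonian-Laird, with a Hartung-Knapp t interval on 6 df) covered the mean 97%, 96% and 96% of the time at the three SDs. Its nominal 95% prediction interval for a new site covered 87%, 88% and 90%. With no between-site variation, the interval for the mean had half-width about 2.7 points and coverage 99%.

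**The case against.** The strongest reply is that the plan already deals with this. Section 9.3 plans random-effects models for exactly these rates and intends to use between-site variability in powering Phase III, and the exact site-level intervals will show the spread. A reader might infer that the plan ignores between-site variation. The documents do not support that: what is missing is a link between sections, not an analysis.

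Second, the pooled interval is valid for the screened cohort, and 9.2 speaks of recruitment at the SCA sites. Nothing in the plan applies ±2 points to a new site. This stands, and it is why the interval should be kept and labelled. Section 10.1.4 could equally be served by the 9.3 model, since it names no method.

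Third, the number of sites a later trial needs also depends on volume and consent. Listed volumes alone run from 40 to 200, so the yield interval is only one input. This also stands.

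Fourth, the size rests on assumed SDs and on all seven sites screening throughout, although 9.2 adds two of them later. With fewer sites the shortfall is larger, not smaller.

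A reader might also infer that the yearly milestones in 10.1.2 conflict with 9.2. Mostly they do not. Fifty screened is a floor, and 333/5 = 67 screened × 15% = 10 enrolled per site, which matches the milestone and fits less than one case per site per month. Seven sites × 10 = 70 against 50 a year is margin from sites added to help enrollment. What remains is that one site's listed volume of 40 is below the floor of 50. Section 8 names further screening sources, so this calls only for reconciling the passages.

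**Conclusion.** The point holds as one of precision and analysis method, at low severity. The ±2 points is not an arithmetic error: it reproduces as a simple binomial. The one figure to correct is ±1.5 at 10% prevalence, which is about ±1.65.

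For the mean yield across sites, ±2 points is too narrow once yields differ between sites. How much too narrow cannot be settled from the documents. Under the assumed SDs the half-width is 1.6 to 2.7 times the stated 2 points (3.3/2 to 5.4/2), and part of that ratio reflects the small-sample method. It would be wrong to conclude that the pooled interval is invalid, because it keeps its coverage for the cohort actually screened.

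**What to change.** 1. In 9.1 and 9.4.1, label the pooled exact interval as descriptive of the screened cohort, and keep the exact site intervals. State that the overall inferential estimate comes from the 9.3 random-effects model: mean yield with a small-sample t interval, the between-site SD, and a prediction interval for a new site, described as approximate.
2. In 9.2, state that ±2 points assumes no between-site variation, change ±1.5 to about ±1.65, and add half-widths over a stated range of site SDs.
3. Optionally, reconcile the screening floor of 50 in 10.1.2 with the listed volume of 40 in 9.2.

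The cost is text plus output from a model already planned, with no extra patients. The stated precision becomes less favourable. If sites are in fact homogeneous, the model-based interval is somewhat conservative (about 2.7 points against 1.95). With seven sites the between-site SD will be poorly estimated, so the prediction interval will fall short of its nominal level.

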Moderate to severe disability after SH has been reported in 11-22% of patients^{17, 40-42}. A CA re-bleed causes significantly greater disability than initial SH²². The proportion of CASH cases with any functional disability varied between 26 and 65% at U Chicago, Mayo and BVMC cohorts. Only two studies assessed QOL in CAs, and both were limited to surgical patients. One study⁴³ used Karnofsky performance scale, Patzold Rating and SF-36, and the second⁴⁴ used only SF-36. Newer QoL scores (e.g. EQ-5D and PROMIS 29) have been validated and are more specific for stroke patients compared to SF-36⁴⁵⁻⁵³, and easier to obtain than the Patzold Rating⁵⁴. No study to date has reported QOL measures or their changes over time in CASH patients observed without surgery. **It would be useful to assess functional outcome and QOL measures at baseline and document their change over time with or without a symptomatic re-bleed.** One or more may be fit for use as a putative outcome in clinical trials of pharmacotherapies, and may even be useful in future surgical trials. As to the QSM and DCEQP biomarkers of lesional hemorrhage and permeability, even if they are successfully and reliably deployed at multiple sites, **it remains unclear how they change during longitudinal follow-up in cases with CASH, and whether their changes are more sensitive than clinical events.** The gaps of knowledge regarding outcome measures in clinical trials are addressed in Specific Aim 3 of this proposal.

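### The Aim 1 quality-of-life analyses (Spearman with mRS, and mean scores by mRS level) cannot determine or quantify a ceiling effect, which the plan says they will do

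*Combined protocol and SAP*

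**What the plan says.** Section 9.1 (Specific Aim 1) names two analyses for the baseline quality-of-life scores. The first is a rank correlation: "Spearman correlation coefficients will be calculated between mRS and Euro-QoL and PROMIS29 scales". The second is a table of means: "mean scores of Euro-QoL and PROMIS29 will be stratified by mRS levels". The plan then says what these deliver: "This analysis will allow us to determine ceiling effects of scores and how well the Euro-QoL and PROMIS29 data are distributed in CASH cases". Section 9.4.1 names the same two analyses and draws the same conclusion: "This analysis will allow us to determine ceiling effects of scores". It adds a wider claim: "Baseline Euro-QoL and PROMIS29 measures will be validated for use in CAs".

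Neither section names the percentage at the best score, a histogram, quantiles or a limit for calling a ceiling. Section 9.1 does open with frequencies and ranges, but for data cleaning: "Descriptive statistics (frequencies, min, max, mean, standard deviation) and contingency table analysis will be performed to identify any possible coding errors". That sentence has no counterpart in section 9.4.1. Both sections also give impairment bands in SD units below a reference mean.

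On the population, section 4.2 reports: "The proportion of CASH cases with any functional disability varied between 26 and 65% at U Chicago, Mayo and BVMC cohorts".

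**The concern.** A ceiling effect is a statement about one part of a distribution: how many patients already have the best attainable score. A mean averages over that part. A rank correlation describes how two orderings agree. The plan therefore promises a result that the analyses it names do not produce.

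This matters because section 4.2 assigns to Aim 1 the question of which functional and quality-of-life instruments best capture the impact of the disease. Section 3 says that results will endorse or reject outcome instruments, and the milestone table in section 10.1.2 foresees an application to the FDA for one or more of them. Patients enter within a year of a bleed, so some may recover during follow-up. A patient who starts at the best score cannot register that recovery. A reader who takes the stated analysis at its word could believe that this had been examined when it had not.

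**Working it through.** **No figure to reproduce.** The documents give no ceiling limit, no expected share at the best score, and no precision target for this analysis. The check is whether the two named summaries can fix the share at the maximum.

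**1. Is a ceiling plausible?** Section 4.2 gives any functional disability as 26% to 65%. The complement is 100 - 65 = 35% to 100 - 26 = 74% without disability. Section 9.2 says "we propose recruiting 200 CASH cases for the SCA arm of this project", so this is 0.35 × 200 = 70 to 0.74 × 200 = 148 patients.

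**2. Stratum means.** Let *M* be the best score, *c* the share at *M*, and *L* the mean of the others. Then mean = *cM* + (1 - *c*)*L*. Take an assumed scale of 0-100 and a stratum mean of 90:
- *c* = 0, *L* = 90: mean 90.
- *c* = 0.5, *L* = 80: 0.5 × 100 + 0.5 × 80 = 90.

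The planned table shows 90 in both cases.

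**3. Means and rank correlation together.** Two score distributions were simulated, with 200,000 patients each. The assumptions are means of 90, 80, 68, 55 and 40 at mRS 0 to 4; 35% or 74% of patients at mRS 0; and the remainder split 50/25/15/10% over mRS 1 to 4. In the ceiling version, half of mRS 0 and a fifth of mRS 1 score 100. In the other version nobody does, and its spread was chosen so that rho matches.

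| At mRS 0 | Version | rho | At maximum | At 99 or above |
|---|---|---|---|---|
| 35% | ceiling | -0.743 | 24.0% | 24.0% |
| 35% | no ceiling | -0.743 | 0% | 2.6% |
| 74% | ceiling | -0.560 | 39.6% | 39.6% |
| 74% | no ceiling | -0.557 | 0% | 7.7% |

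Stratum means agree to within about 0.2 points. The ceiling shares can be checked by hand: 0.35 × 0.5 + 0.65 × 0.5 × 0.2 = 0.240, and 0.74 × 0.5 + 0.26 × 0.5 × 0.2 = 0.396.

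A narrower no-ceiling distribution with the same means gave rho of -0.833 (35% at mRS 0) and -0.647 (74%). So rho moves with the spread of scores even when nobody is at the maximum, and its value cannot be read as evidence for or against a ceiling.

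**4. What the means can show.** If the next attainable score below 100 were 95 (an assumption), the share at the maximum would be at least (mean - 95)/5. A mean of 97 gives (97 - 95)/5 = 40%. A mean of 95 or below gives a lower bound of 0. A mean almost at the maximum is therefore informative, and lower means are not.

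**5. What direct reporting would give.** Exact (Clopper-Pearson) 95% intervals for a share at the best score, n = 200:

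| Observed | 95% CI |
|---|---|
| 5% | 2.4-9.0% |
| 15% | 10.4-20.7% |
| 35% | 28.4-42.0% |
| 50% | 42.9-57.1% |

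Within an mRS level the intervals widen roughly with the square root of the sample-size ratio. For 70 patients the factor is √(200/70) = 1.69, so the half-width at 15% goes from about 5 to about 9 percentage points.

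**The case against.** The strongest reply is that the information will exist anyway. Frequencies, minimum and maximum are listed in section 9.1, the impairment bands describe the distribution beyond the mean, and section 10.1.4 says that statisticians will refine the plans in year 1. The share at the best score can be computed at any time from collected data. This stands as a reason to rate the point modestly. It does not remove it: the frequencies serve error checking and carry no ceiling criterion, the bands grade scores worse than the reference mean, and the plan attributes the ceiling result to other statistics.

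Three stronger readings are tempting, and the documents do not support them.

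- A reader might infer that the planned means can never reveal a ceiling. They can when a stratum mean lies almost at the maximum. What fails is determining or quantifying one in general.
- A reader might take 35-74% as the expected share at the ceiling. It is a complement derived from three cohorts whose definition of disability is not given. Section 9.4.1 describes PROMIS29 as covering anxiety, depression and fatigue, which a patient without functional disability may still have.
- A reader might infer that instruments will be wrongly endorsed, or that the re-bleed comparisons are compromised. No section makes the Spearman result an endorsement rule, and the documents do not show whether a ceiling would make an instrument look better or worse on that correlation. Section 4.2 assigns the outcome-measure gaps to Aim 3, which compares changes with and without re-bleeding. Patients at the best score still have room to worsen.

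**Conclusion.** The point holds in a limited form. Sections 9.1 and 9.4.1 state a method that does not deliver its claimed output: identical stratum means and nearly identical rho are compatible with 0% or with 24-40% of patients at the maximum. Those percentages come from a constructed example on an assumed 0-100 scale with assumed mRS proportions. They prove that the summaries do not identify a ceiling, and they do not forecast one. The documents support that a ceiling is plausible and give no basis for its size.

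This is a secondary, descriptive item of Aim 1. Its consequence is mainly for judging whether the instruments can show improvement. It is worth correcting because the plan intends to validate these instruments and to decide on their use.

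**What to change.** In sections 9.1 and 9.4.1:

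- For EQ-5D and each PROMIS29 domain, report the number and percentage of patients at the best and at the worst attainable score, with exact 95% confidence intervals, overall and by mRS level. Note that the mRS strata will be less precise.
- State the scoring metric actually used for EQ-5D and its best and worst attainable values. The sections refer to a T-score metric and do not give these end points.
- Show the score distribution (histogram or quantiles) alongside.
- Agree a limit for calling a ceiling before the analysis, and say whether it applies to the estimate or to a confidence limit. The documents give none. If 15% were chosen (an assumption), an observed 15% of 200 would carry an interval of 10.4-20.7%.
- Keep the Spearman coefficients as convergent validity only, and delete the statement that they and the stratified means determine ceiling effects.

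The cost is one extra descriptive table and edited wording in two sections. No additional patients, visits or data are needed.
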